**Table 6 Highly Effective Contraceptive Methods**

Highly Effective Contraceptive Methods That Are User Dependent  Failure rate of <1% per year when used consistently and correctly.

Combined (estrogen- and progestogen-containing ) hormonal contraception associated with inhibition of ovulationb
 
 
• oral
 
• intravaginal
 
• transdermal
 

Progestogen-only hormonal contraception associated with inhibition of ovulation
 
 
• injectable
 

Highly Effective Methods That Are User Independent

 
• Implantable progestogen-only hormonal contraception associated with inhibition of ovulationb
 
• Intrauterine device (IUD)
 
• Intrauterine hormone-releasing system (IUS)
 
• bilateral tubal occlusion
 

Vasectomized partner
 
(A vasectomized partner is a highly effective contraception method provided that the partner is the sole male sexual partner of the WOCBP and the absence of sperm has been confirmed. If not, an additional highly effective method of contraception should be used.)

Sexual abstinence
 
(Sexual abstinence is considered a highly effective method only if defined as refraining from heterosexual intercourse during the entire period of risk associated with the study drug. The reliability of sexual abstinence needs to be evaluated in relation to the duration of the study and the preferred and usual lifestyle of the participant.)

NOTES:

 Typical use failure rates may differ from those when used consistently and correctly. Use should be consistent with local regulations regarding the use of contraceptive methods for participants in clinical studies.

 Hormonal contraception may be susceptible to interaction with the study drug, which may reduce the efficacy of the contraceptive method. In this case two highly effective methods of contraception should be utilized during the treatment period and for at least 48 h after the last dose of study treatment

**Pregnancy Testing**

- WOCBP should only be included after a confirmed menstrual period and a negative highly sensitive urine pregnancy test at the times listed in the SoA (Section 2)

- Additional pregnancy testing is not required during the treatment period and at 48 h after the last dose of study treatment
- Pregnancy testing will be performed whenever a menstrual cycle is missed or when pregnancy is otherwise suspected
- Pregnancy testing, with a sensitivity of 2 mIU/mL will be performed using the test kit provided by the central laboratory.

### **Collection of Pregnancy Information**

#### **Female Participants who become pregnant**

- Investigator will collect pregnancy information on any female participant, who becomes pregnant while participating in this study.
- Information will be recorded on the appropriate form and submitted to GSK within 24 h of learning of a participant's pregnancy.
- Participant will be followed to determine the outcome of the pregnancy. The investigator will collect follow up information on participant and neonate, which will be forwarded to GSK. Generally, follow-up will not be required for longer than 6 to 8 weeks beyond the estimated delivery date.
- Any termination of pregnancy will be reported, regardless of fetal status (presence or absence of anomalies) or indication for procedure.
- While pregnancy itself is not considered to be an AE or SAE, any pregnancy complication or elective termination of a pregnancy will be reported as an AE or SAE.
- A spontaneous abortion is always considered to be an SAE and will be reported as such.
- Any SAE occurring as a result of a post-study pregnancy which is considered reasonably related to the study treatment by the investigator, will be reported to GSK as described in [Appendix 6](#). While the investigator is not obligated to actively seek this information in former study participants, he or she may learn of an SAE through spontaneous reporting.

Any female participant who becomes pregnant while participating will be withdrawn from the study.

## 12.7. Appendix 7: Liver Safety: Required Actions and Follow-up Assessments

For the purposes of this protocol, please refer to the guidelines below for the required action, monitoring and follow-up assessments if a participant meets any of the criteria listed below, after dosing with the study medication.

### Phase I liver chemistry stopping criteria and required follow up assessments for Healthy Volunteer Participants

Liver Chemistry Stopping Criteria	
ALT-absolute	
ALT<math>\geq</math>3xULN
 
If ALT<math>\geq</math>3xULN AND bilirubin <math>\geq</math> 2xULN (>35% direct bilirubin) or INR >1.5, Report as an SAE.
 
See additional Actions and Follow Up Assessments listed below

Required Actions and Follow up Assessments	
Actions	Follow Up Assessments

 
Report the event to GSK within 24 h
 
Complete the liver event CRF, and complete an SAE data collection tool if the event also meets the criteria for an SAE
 
Perform liver event follow up assessments
 
Monitor the participant until liver chemistries resolve, stabilise, or return to within baseline (see MONITORING below)
 
 
MONITORING:
 
If ALT<math>\geq</math>3xULN AND bilirubin <math>\geq</math> 2xULN or INR >1.5
 
 
Repeat liver chemistries (include ALT, AST, alkaline phosphatase, bilirubin) and perform liver event follow up assessments within 24 h
 
Monitor participants twice weekly until liver chemistries resolve, stabilise or return to within baseline
 
A specialist or hepatology consultation is recommended
 
 
If ALT<math>\geq</math>3xULN AND bilirubin < 2xULN and
	
 
Viral hepatitis serology
 
Obtain INR and recheck with each liver chemistry assessment until the transaminases values show downward trend
 
Obtain blood sample for pharmacokinetic (PK) analysis, obtained 48 h of last dose
 
Serum creatine phosphokinase (CPK) and lactate dehydrogenase (LDH).
 
Fractionate bilirubin, if total bilirubin<math>\geq</math>2xULN
 
Obtain complete blood count with differential to assess eosinophilia
 
Record the appearance or worsening of clinical symptoms of liver injury, or hypersensitivity, on the AE report form
 
Record use of concomitant medications on the concomitant medications report form including acetaminophen, herbal remedies, other over the counter medications.
 
Record alcohol use on the liver event alcohol intake case report form
 

Liver Chemistry Stopping Criteria	

INR ≤1.5:
 
 
Repeat liver chemistries (include ALT, AST, alkaline phosphatase, bilirubin) and perform liver event follow up assessments within 24-72 h
 
Monitor participants weekly until liver chemistries resolve, stabilize or return to within baseline
 
	
If ALT ≥3xULN AND bilirubin ≥ 2xULN or INR >1.5:
 
 
Anti-nuclear antibody, anti-smooth muscle antibody, Type 1 anti-liver kidney microsomal antibodies, and quantitative total immunoglobulin G (IgG) or gamma globulins.
 
Serum acetaminophen adduct high performance liquid chromatography (HPLC) assay (quantifies potential acetaminophen contribution to liver injury in participants with definite or likely acetaminophen use in the preceding week [James, 2009])
 
Liver imaging (ultrasound, magnetic resonance, or computerised tomography) and /or liver biopsy to evaluate liver disease; complete Liver Imaging and/or Liver Biopsy CRF forms.
 

- Serum bilirubin fractionation should be performed if testing is available. If serum bilirubin fractionation is not immediately available, discontinue study treatment for that participant if ALT ≥ 3xULN and bilirubin ≥ 2xULN. Additionally, if serum bilirubin fractionation testing is unavailable, record presence of detectable urinary bilirubin on dipstick, indicating direct bilirubin elevations and suggesting liver injury.
- All events of ALT ≥ 3xULN and bilirubin ≥ 2xULN (>35% direct bilirubin) or ALT ≥ 3xULN and INR>1.5, if INR measured, which may indicate severe liver injury (possible 'Hy's Law'), must be reported as an SAE (excluding studies of hepatic impairment or cirrhosis); INR measurement is not required and the threshold value stated will not apply to participants receiving anticoagulants
- Includes: Hepatitis A IgM antibody; Hepatitis B surface antigen and Hepatitis B Core Antibody (IgM); Hepatitis C RNA; Cytomegalovirus IgM antibody; Epstein-Barr viral capsid antigen IgM antibody (or if unavailable, obtain heterophile antibody or monospot testing); Hepatitis E IgM antibody
- PK sample may not be required for participants known to be receiving placebo or non-GSK comparator treatments. Record the date/time of the PK blood sample draw and the date/time of the last dose of study treatment prior to PK blood sample draw on the CRF. If the date or time of the last dose is unclear, provide the participant's best approximation. If the date/time of the last dose cannot be approximated OR a PK sample cannot be collected in the time period indicated above, do not obtain a PK sample. Instructions for sample handling and shipping are in the SRM.

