## 1. SYNOPSIS

**Protocol Title:** A Phase 1, open-label, non-randomized, parallel group, single-dose adaptive study in adults with hepatic impairment and matched, healthy control participants with normal hepatic function.

**Short Title:** Daprodustat hepatic impairment study

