#### **6.2.1.1. Additional Exclusion Criteria for Hepatically-Impaired Participants**

#### **CONCURRENT CONDITIONS/MEDICAL HISTORY**

1. Presence of 8 times ULN elevations in AST, ALT, or bilirubin.
2. Participants with any other medical condition which, in the judgment of the investigator and Medical Monitor, could jeopardize the integrity of the data derived from that participant or the safety of the participant.
3. Participants with advanced ascites (Grade 3).
4. Participants with refractory encephalopathy as judged by the investigator or significant Central Nervous System (CNS) disease (e.g., dementia, or seizures) which the investigator considers will interfere with the informed consent, conduct, completion, or results of this trial or constitutes an unacceptable risk to the participant.
5. Participants with functional Transjugular Intrahepatic Portosystemic Shunt (TIPS) placement.
6. Presence of hepatopulmonary or hepatorenal syndrome.
7. Presence of primarily cholestatic liver diseases.
8. History of liver transplantation.
9. Participants with signs of active infection, including active spontaneous bacterial peritonitis.
10. Participants with unstable cardiac function or participants with hypertension

- whose blood pressure is not controlled (based on the investigator's discretion).
11. Diabetic participants whose diabetes is not controlled (based on the investigator's discretion).

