## **8. DISCONTINUATION CRITERIA**

### **8.1. Discontinuation of Study Treatment**

#### **8.1.1. Liver Chemistry Stopping Criteria**

**Liver chemistry stopping and increased monitoring criteria** have been designed to assure participant safety and evaluate liver event etiology (in alignment with the FDA premarketing clinical liver safety guidance). These protocol guidelines are in alignment with FDA premarketing clinical liver safety guidance:

<http://www.fda.gov/downloads/Drugs/GuidanceComplianceRegulatoryInformation/Guidances/UCM174090.pdf>.

Discontinuation of study treatment for abnormal liver tests in the healthy control participant cohorts is required when:

- a participant meets one of the conditions outlined in the algorithm;

OR

- when in the presence of abnormal liver chemistries not meeting protocol-specified stopping rules, the investigator believes study treatment discontinuation is in the best interest of the participant.

The liver chemistry stopping criteria for healthy control participants can be found in [Appendix 7](#).

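### Appendix 7 orders SAE reporting of possible Hy's Law events in healthy controls, but its own footnote exempts hepatic impairment studies, which this trial is

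*Protocol*

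**What the plan says.** Section 8.1.1 of the protocol addresses the healthy cohorts: "Discontinuation of study treatment for abnormal liver tests in the healthy control participant cohorts is required when" a participant meets the algorithm or the investigator judges it necessary. It sends the reader to Appendix 7, whose table is titled for "required follow up assessments for Healthy Volunteer Participants".

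That table says three relevant things:

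- **Criterion row.** ALT at least 3xULN together with bilirubin at least 2xULN (more than 35% direct) or INR above 1.5: "Report as an SAE". The bilirubin term carries footnote marks 1 and 2.
- **Actions column.** "Report the event to GSK" within 24 h and fill in the liver event form. Then "complete an SAE data collection tool if the event also meets the criteria for an SAE", again marked with footnote 2.
- **Footnote 2.** Events meeting the same combined criterion "must be reported as an SAE (excluding studies of hepatic impairment or cirrhosis").

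Note 1 to Table 5 in Appendix 3 repeats the exemption in the same words. The protocol's short title is "Daprodustat hepatic impairment study".

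**The concern.** The row and the footnote attached to it point in different directions for the same person. The row tells the site to report a healthy control's event as serious. The footnote restates that duty and then removes it for a class of studies to which this trial belongs. The exemption is worded by study, not by participant or cohort, so its literal reach includes the controls.

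An exemption makes sense for impaired participants, whose underlying disease can put them above the triggers before dosing. It makes no sense for controls, who must be judged healthy on laboratory tests among other things and are excluded for hepatitis B surface antigen or a positive hepatitis C antibody. In a control, known liver disease would not explain the event.

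What depends on the answer is whether the following apply by rule or only by judgment: the SAE form, the 72 h causality verification in Appendix 5, the regulatory route in Section 9.2.5, and counting in Tables 2.4 and 2.5 of the SAP. Two sites reading the same page could classify identical events differently.

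**Working it through.** There is no figure in the plan to reproduce. The check is a comparison of texts followed by two small counts.

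**1. Does the exemption reach this trial?** It covers hepatic impairment studies. The title and short title make this one. Yes.

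**2. Does it reach healthy controls?**

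| Text | Who it covers | Instruction on the combined criterion |
|---|---|---|
| Appendix 7, criterion row | Healthy volunteers | Report as serious, without condition |
| Appendix 7, actions column | Healthy volunteers | SAE form if SAE criteria are met; see footnote 2 |
| Appendix 7, footnote 2 | No participant limit | Mandatory, except in hepatic impairment or cirrhosis studies |
| Appendix 3, Table 5, note 1 | No participant limit | Same as footnote 2 |
| Section 8.1.1 | Healthy control cohorts | Points to Appendix 7; silent on SAE status |
| Appendix 5, other situations | Everyone | Left to medical judgment |

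One row mandates reporting, two notes exempt the study, and nothing confines the exemption to impaired participants. The actions column does not break the tie, because its footnote mark returns the reader to the exemption.

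**3. Is this current text?** Yes. The original protocol has the same wording, and the Amendment 1 summary lists no change to this rule in Appendix 3 or 7.

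**4. Why would an exemption exist?** Section 6.2.1.1 excludes impaired participants for "Presence of 8 times ULN elevations in AST, ALT, or bilirubin". The limit of 8xULN lies above both the ALT trigger (3xULN) and the bilirubin trigger (2xULN), so an impaired participant can enter already past those values. The bilirubin arm also needs more than 35% direct bilirubin, so entry above 2xULN does not by itself complete the criterion. This supports a participant-level exemption; it gives no reason to exempt controls.

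**5. How many people does the affected table cover?** Planned controls: 8 / (8 + 8) = 8/16 = 50% in Part 1. If Part 2 runs: (8 + 8) / (16 + 16) = 16/32 = 50%. These are planned numbers; the protocol asks for at least 8 per cohort and replacements are possible. They count people covered, not expected events.

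**6. What differs between the two readings?**

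| Step for a control meeting the combined criterion | Row prevails | Footnote prevails |
|---|---|---|
| Sponsor told within 24 h | Yes | Yes |
| Liver event form, follow-up, monitoring | Yes | Yes |
| Conditional liver listings in the SAP | Yes | Yes |
| SAE status | Automatic | By judgment |
| SAE form, 72 h causality check, Section 9.2.5, Tables 2.4 and 2.5 | By rule | Only if judged serious |

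**The case against.** The best reply is that the footnote does not contradict the row. Its parenthesis narrows the footnote's own general duty and nowhere says not to report. The row is a separate, direct order in a table for healthy volunteers, and reading the exemption as covering everyone would leave that order with nobody to apply to in this trial. A sensible site would follow the row. This is probably the intended meaning. It does not settle the text, because a footnote marked on a criterion ordinarily qualifies it, and the document never says the row prevails.

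The second reply is that little turns on it. That stands. First notice to the sponsor is due within 24 h either way, since Section 9.2.1 sets the same limit for SAEs. Judgment can still make the event serious. Scheduled laboratory tests after dosing fall only at 48 h and follow-up. PT/INR is listed with the screening tests, so the INR arm would normally arise only after ALT had already triggered follow-up. The pharmacokinetic endpoints and the Part 2 decision are untouched.

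Third, the SAP does set separate liver thresholds for healthy and impaired subjects (Section 10.7.1), but these are display flags for values of potential clinical importance, not SAE reporting rules. That is correct; they show only that the plan distinguishes the groups elsewhere, and the point does not rest on them.

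**Conclusion.** The inconsistency is real and the wording is wrong as it stands, at low severity. For a healthy control with a possible Hy's Law event, the protocol both orders SAE reporting and, read literally, exempts the study from it.

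The open question is confined to automatic SAE classification and what follows from it. The documents give no event rate. They describe single doses up to 500 mg in healthy participants as generally well tolerated, against one 6 mg dose here, so few or no cases are expected. No missed safety signal and no effect on the pharmacokinetic results is claimed.

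The conclusion assumes that footnote 2 qualifies the criterion it is marked on, and that the intent is to exempt participants whose liver disease already raises these tests.

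**What to change.** In Appendix 7 footnote 2 and Appendix 3 Table 5 note 1, change *studies of* to *participants with*, so that the exemption covers participants with hepatic impairment or cirrhosis. Alternatively, delete the parenthesis in Appendix 7, which covers controls only, and make the replacement in Table 5 note 1.

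Either version makes SAE reporting automatic for controls and keeps the exemption for impaired participants. The cost is one phrase in each of two notes, with no change to visits, data collection or analysis.

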**12.8. Appendix 8: Grades of Hepatic Encephalopathy**

Grade	Description
1	Trivial lack of awareness, euphoria or anxiety; shortened attention span; impairment of addition or subtraction
2	Lethargy; disorientation for time; obvious personality changes; inappropriate behavior
3	Somnolence to semistupor; responsive to stimuli; confused; gross disorientation; bizarre behavior
4	Coma; unable to test mental state

**12.9. Appendix 9: Protocol Amendment History**

The Protocol Amendment Summary of Changes Table for the current amendment is located directly before the Table of Contents (TOC).

1. REPORTING & ANALYSIS PLAN SYNOPSIS

Overview	Key Elements of the Reporting and Analysis Plan
Purpose	
The purpose of this reporting and analysis plan (RAP) is to describe:
 
 The planned analyses and output to be included in the Clinical Pharmacology Study Report for Protocol 200231. This RAP is intended to describe the safety and pharmacokinetic (PK) analyses required for the study which will be provided to the study team members to convey the content of the reporting efforts, specifically Statistical Analysis Complete (SAC).
Protocol	
 This RAP is based on original protocol (Dated: [23-May-2017]) for study 200231 [GlaxoSmithKline Document Number: 2016N305941_00].
Primary Objectives	
 To compare plasma PK parameters of daprodustat and its six metabolites (GSK2391220 (M2), GSK2506104 (M3), GSK2487818 (M4), GSK2506102 (M5), GSK2531398 (M6), and GSK2531401 (M13)) in participants with hepatic impairment to healthy controls matched in gender, age, and body mass index (BMI). To evaluate the impact of hepatic impairment on the plasma protein binding and unbound concentration of daprodustat in plasma.
Primary Endpoints	
 Daprodustat and its metabolites in plasma area under the concentration-time curve from time zero (predose) extrapolated to infinite time [AUC (0-∞)], percentage of AUC (0-∞) obtained by extrapolation (%AUC_{ex}), time zero (predose) to time of last quantifiable concentration [AUC(0-t)], maximum observed concentration (C_{max}) following a single oral dose of daprodustat, apparent terminal phase half-life (t_{1/2}), and time of occurrence of C_{max} (T_{max}) following a single oral dose of daprodustat. Unbound concentration and unbound fraction in plasma of daprodustat at 3, 12, and 24 hours (h) post dose (as data permit).
Secondary Objectives	
 To characterize the effect of hepatic impairment on the pharmacodynamics (PD) effect of daprodustat. To assess the safety and tolerability of a single 6 mg dose of daprodustat.

Overview	Key Elements of the Reporting and Analysis Plan
Secondary Endpoints	
 • Maximum observed erythropoietin concentration (C_{max}, EPO), Time of the maximum observed erythropoietin concentration (T_{max}, EPO) and erythropoietin area under the concentration-time curve from time zero (pre-dose) to the last time of quantifiable erythropoietin concentration [AUC (0-t, EPO)]. • Safety and tolerability parameters, including adverse events and clinical laboratory tests.
Study Design	
 • A phase 1, open-label, non-randomized, parallel group, single-dose adaptive study in adults with moderate (Part 1) and either mild or severe (Part 2) hepatic impairment and matched, healthy control participants with normal hepatic function. 
Part 1:
 
 • Part 1 will include 2 cohorts. Cohort 1 includes participants with moderate hepatic impairment, and Cohort 2 includes matched healthy control participants. • Healthy control participants (n=8) will be matched in gender, age (± 10 years), and BMI ($\pm 15\%$) to participants with moderate hepatic impairment (n=8; Child-Pugh score of 7-9). • All participants will receive 6 mg of daprodustat as a single oral dose in the fasted state. • Up to 16 participants (8 in each cohort, excluding possible replacements) will be recruited into Part 1 of the study. 
Part 2:
 
 • Part 2 will include 2 cohorts. Cohort 3 includes participants with either mild or severe hepatic impairment, and Cohort 4 includes matched healthy control participants. • Healthy control participants (n=8) will be matched in gender, age (± 10 years), and BMI ($\pm 15\%$) to participants with either mild impairment (Child-Pugh score of 5-6) or participants with severe impairment (Child-Pugh score of 10-13) (n=8). • All participants will receive 6 mg of daprodustat as a single oral dose in the fasted state. • Up to 16 participants (8 in each cohort, excluding possible replacements) will be recruited into Part 2 of the study. • All participants' total involvement with the study will be up to 7 weeks.
Planned Analyses	
 • An informal interim analysis of the primary PK endpoints of AUC (0-∞), AUC(0-t) and C_{max} will be conducted for completion of Part 1 of the study. • The final planned analyses will be performed, as defined in this RAP document, after database freeze has been declared. • Safety and PK/PD data will be presented in tabular and/or graphical format and summarized descriptively according to GSK's Integrated Data

Overview	Key Elements of the Reporting and Analysis Plan
	Standards Library (IDSL) standards.
Analysis Population	
 • Screened Population: All participants who were screened will be considered for this population. This population will be used for summarizing screening status. • Enrolled Population: All participants who were successfully screened and enrolled for the trial and for whom a record exists on the study database. This population will be used for summarize number of subjects by Country and Site ID and age ranges. • Safety Population: All participants who received at least 1 dose of study medication. This will be the primary population for the safety analyses. • PK Population: All participants in the ‘Safety Population’ for whom a PK sample has been obtained and analyzed will be included in the PK population. This population will be used in the evaluation of PK data. PK samples that may be affected by protocol deviations will be reviewed by the study team to determine whether or not the sample will be excluded from the analyses of PK data. • PD Population: All participants in the ‘Safety Population’ who had at least 1 PD assessment. PD samples that may be affected by protocol deviations will be reviewed by the study team to determine whether or not the sample will be excluded from the analyses of PD data.
Hypothesis	No formal hypotheses will be tested.
Interim Analyses	
An informal interim analysis of the primary PK endpoints AUC (0-∞), AUC(0-t) and Cmax will be conducted following completion of Part 1 of the study, with possible progression to Part 2 based on the following criteria:
 
 ➤ If a < 2-fold change in daprodustat exposure (AUC) is observed in participants with moderate hepatic impairment compared to the healthy matched control group, the study may enrol participants with severe hepatic impairment and a healthy, matched control group. ➤ If a ≥ 2-fold change in daprodustat exposure (AUC) is observed in participants with moderate hepatic impairment compared to the healthy matched control group, the study may enrol participants with mild hepatic impairment and a healthy, matched control group.

